Patients will discontinue Qsymia the week prior to the scheduled operation. The sleeve gastrectomy will be performed by one of the surgeons at the Weight Management Center ([name], [name], [name]) using standard laparoscopic technique. Post-operatively, all patients will be provided with dietary counseling and a nutrition prescription for a very low calorie, high protein diet: 500-700 calories, protein goal of 1-1.2g/kg IBW, and 60-75g carbohydrate. Qsymia will be resumed in the second post-operative week at the initial titration dose and increased to the recommended treatment dose of 7.5/46 mg daily. Patients will have standard post-operative surgical follow up at months 1, 3, 6, 9, 12, 18, and 24. During the post-operative phase, all patients will be enrolled in the bariatric support group program that meets on a monthly basis. Patients will also have at least 3 visits with a clinic dietitian to review and update dietary prescriptions. At any point during this course of follow up, a determination can be made that the primary outcome event has occurred if the patient has a weight plateau—defined as weight gain or < 3 lbs weight loss—for 3 consecutive months, remains above a BMI of 39.9 kg/m² and continues to have associated co-morbidities. These patients will be evaluated for the possibility of moving forward to the next operative stage (laparoscopic Roux-en-Y gastric bypass) while all other patients will continue on with medication and diet/exercise therapy.

Control Group

Control subjects for the proposed study will be identified from the patient population at the Wake Forest Baptist Health Weight Management Center. They will be matched to subjects in the treatment group on age, sex, ethnicity, and BMI. They will be a historical control group who had surgery prior to the commencement of the proposed study (retrospective review).

Trial Design

Prospective independent historical case control

Inclusion Criteria

Inclusion criteria for the proposed study are:

- BMI \geq 50 kg/m²
- Determined to be a good candidate for surgery based on medical and psychological exam.
- Willing to participate in a 3-6 month medically supervised weight loss plan prior to surgery.
- Planning to remain in the reasonable vicinity of the Wake Forest Baptist Health Weight Management Center for the duration of the study.

Exclusion Criteria

- History of prior weight loss surgery (removal/conversion from band to sleeve will not be excluded)

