- Pregnant (women of childbearing potential will complete a pregnancy test (blood draw) to make sure they are not pregnant at the time that they initiate the medication). Ongoing monitoring of pregnancy status is the responsibility of the patient and they are instructed as such in the consent form.
- Ongoing use of weight loss medication
- Contraindications to use of Qsymia, including pregnancy, history of glaucoma, unstable cardiac disease (unstable angina, recent heart attack or stroke (in the past 6 months), uncontrolled arrhythmia), hyperthyroidism, taking MAOIs (monoamine oxidase inhibitors) or allergy to either topiramate or sympathomimetic amines like phentermine.

Patients may be removed from the study at any point if they are unable to tolerate the study medication or are less than 50% compliant with the study medication (take less than 50% of the recommended dose). If a patient is removed from the study due to medication intolerance or non-compliance, the study physician will meet with them and instruct them on how to stop the medication.

Primary endpoint

The primary endpoint for this study is the proportion of patients that meet the criteria to move forward with the second surgical procedure (Roux en Y Gastric Bypass). The criteria include all of the following at any point in the 24 month post-surgical follow up period:

1. Weight plateau (defined as weight gain or < 3 lbs weight loss) for at least 3 months
2. Remains above a BMI of 39.9 kg/m²
3. Continues to have obesity associated co-morbidities (Co-morbidities include hypertension, type 2 diabetes mellitus or pre-diabetes, hyperlipidemia, metabolic syndrome, obstructive sleep apnea, osteoarthritis, non-alcoholic steatohepatitis (NASH), gastroesophageal reflux disease (GERD)).

We hypothesize that the study group treated with Qsymia plus surgery will have a lower rate of occurrence of the primary endpoint at 24 months post-surgery compared to the group with surgery only.

Secondary endpoints

The secondary endpoints for this study are percent weight loss both before and after surgery and changes in percent body fat and resting metabolic rate.

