We hypothesize that the study group treated with Qsymia plus surgery will have greater percent weight loss at all time points compared to the group treated with surgery only. We also hypothesize that the study group treated with Qsymia plus surgery will have a higher resting metabolic rate after adjustment for lean body mass compared to the group treated with surgery only.

Other measures obtained by chart review

Height will be measured at all new patient visits and will be repeated at 24 months to account for any changes over the course of participation. Weight is measured at every clinic visit and will be captured for the study at the time points in the table below. Waist circumference will be measured at the level of the umbilicus at the time points reported in the table. Resting metabolic rate will be measured using expired gas analysis via the MEDGem analyzer. This will be measured following the protocol suggested by the manufacturer, including after refraining from eating, drinking, caffeine or exercise for at least 4 hours prior and immediately following a 10 minute period of quiet rest. Body fat percentage will be measured using Bioelectrical Impedance Analysis via the RJL Systems Quantum II. The Quantum II provides body fat percentage as well as a calculation of total lean mass and total fat mass.

Blood Measures

Blood will be drawn at baseline, 3 months, 6 months, 12 months, 18 months and 24 months and stored for use in later analysis.

Boxes marked with UC are tests that are done as part of usual care. Boxes marked with R are tests done for research only.

Test	BL	1m	3m	6m	9m	12m	18m	24m
Resting Metabolic Rate (MEDGem Analyzer)	UC			R		R		R
Body Fat % by Bioelectrical Impedance Analysis (RJL Systems)	UC			R		R		R
Height	UC							R
Weight	UC	UC	UC	UC	UC	UC	UC	UC
Waist Circumference	UC			R		R		R
Blood draw	R		R	R		R	R	R

Monitoring of Side Effects to study medication

Monitoring for side effects will be performed at each visit. Report of suicidal ideation will lead to study discontinuation and withdrawal from medication. Endpoint will be considered reached in this instance.

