This is an independent case-control study. Analyses will include completers only. Completers are defined as individuals who enter treatment and continue it (Qsymia and/or gastric sleeve) for at least 24 months without reversal or discontinuation. Participants will be recruited until the sample size of 20 cases is obtained. If a participant consents but does not have surgery, this person will not be counted as a case and thus, recruitment will continue.

Data will be entered into and stored in a REDCap database with access given only to individuals who are part of the study team. Study data uploaded will include information from the weekly clinic questionnaire, adverse events, as well as study outcomes (weight at clinic visits), demographic information, etc.

[figure not shown]
Most of the statistical analyses will be conducted using SPSS or SAS. Prior to testing the specific aims, descriptive statistics will be used to characterize the sample. Next, the groups will be compared using the chi-square statistic and T-test statistic to determine whether differences existed between the groups on key variables that may have an effect on outcomes. The case-control matching procedure should insure balance between the treatment groups on sex, age, BMI and ethnicity, but additional analyses will be used to examine the comparability between groups on baseline body composition, waist circumference, and resting metabolic rate.

The primary endpoint for this study is the proportion of patients that meet the criteria to move forward with the second surgical procedure (Roux en Y Gastric Bypass) at any point during follow up. The proportion of the Qsymia treated group that achieves the primary endpoint will be compared to the surgery only group after 24 months of follow up. Unadjusted and adjusted models will be developed to test for differences in the rate of the primary endpoint occurrence by treatment group.

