The secondary outcomes for this study include percent weight loss and changes in percent body fat and resting metabolic rate. The time points of interest include pre-surgery period (baseline to surgery), baseline to 6 months (post-operative), baseline to 12 months, and baseline to 24 months. Independent T-test statistic will be used to test for differences in the changes scores between the groups at each time point for these continuous variables. Given this pilot study design and exploratory nature of this secondary aim, we will not use the conservative approach of Bonferroni adjustment for multiple comparisons. Therefore, alpha will remain at 0.05 for this family of hypotheses.

Sample size justification/statistical power

We are planning a study with 25 experimental subjects and 20 control subjects. Prior data indicate that the approximate failure rate among controls is 0.7 (Alexandrou et al, 2012). If the true failure rate for experimental subjects is 0.25, we will be able to reject the null hypothesis that the failure rates for experimental and control subjects are equal with probability (power) .840. The Type I error probability associated with this test of this null hypothesis is 0.05. We will use an uncorrected chi-squared statistic to evaluate this null hypothesis.

References

Nguyen, N et al. A review of unmet needs in obesity management. *Obes Surg.* 2012 Jun;22(6):956-66

Alexandrou et al. What is the Actual Fate of Super-Morbid-Obese Patients Who Undergo Laparoscopic Sleeve Gastrectomy as the First Step of a Two-Stage Weight-Reduction Operative Strategy? *Obes Surg* (2012) 22:1623–1628

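### The resting metabolic rate hypothesis is conditional on lean mass, but the only planned test is an unadjusted t-test of change, so the plan does not test it

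*Combined protocol and SAP*

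**What the plan says.** All references are to the combined protocol and SAP.

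- **Hypothesis (Secondary endpoints).** The Qsymia group "will have a higher resting metabolic rate after adjustment for lean body mass compared to the group treated with surgery only". This concerns the level of RMR, conditional on lean mass.
- **Endpoint (Secondary endpoints).** The same section defines the endpoint as "changes in percent body fat and resting metabolic rate", without mention of lean mass.
- **Test (Statistical analysis).** After listing the outcomes ("The secondary outcomes for this study include percent weight loss and changes in percent body fat and resting metabolic rate"), the plan gives them one method: "Independent T-test statistic will be used to test for differences in the changes scores between the groups at each time point".
- **Adjusted models (Statistical analysis).** These are planned for the primary endpoint only: "Unadjusted and adjusted models will be developed to test for differences in the rate of the primary endpoint occurrence by treatment group".
- **Lean mass data (Other measures obtained by chart review).** "The Quantum II provides body fat percentage as well as a calculation of total lean mass and total fat mass". The schedule places bioimpedance alongside RMR at baseline, 6, 12 and 24 months. Both are usual care at baseline and research-only afterwards.
- **Controls (Control Group).** They are historical, operated on before the study began. "They will be matched to subjects in the treatment group on age, sex, ethnicity, and BMI".

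**The concern.** RMR depends partly on how much lean tissue a person carries. A hypothesis about RMR adjusted for lean mass asks whether one group burns more energy than expected for its lean mass. A t-test of raw RMR change asks whether one group's total energy expenditure fell less. Those questions have the same answer on average only if the groups lose the same amount of lean mass.

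The plan gives a reason to doubt that they will. It also hypothesises that the Qsymia group "will have greater percent weight loss at all time points compared to the group treated with surgery only". If some of that extra loss is lean tissue, raw RMR is pulled down in the Qsymia group for a reason that the RMR hypothesis sets aside. Success on the weight hypothesis could then mask, and in some circumstances reverse, the result reported for the RMR hypothesis.

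**Working it through.** **Is the adjustment planned anywhere?** The t-test has no covariates. The adjusted models are confined to the primary endpoint. Baseline body composition and RMR are compared between groups, but only as a comparability check from which no adjustment follows. Matching does not include lean mass, and matching at baseline could not account for lean mass lost later. So the adjustment named in the hypothesis appears in no planned analysis. The plan states no effect size, SD or power for RMR, so it has no figure to reproduce.

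**Size of the discrepancy.** Let τ be the lean-mass-adjusted RMR difference (Qsymia minus control), b the kcal/day per kg of lean mass, and d the extra lean mass lost in the Qsymia group. Then

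raw difference = τ − b × d.

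The documents give neither b nor d. Assume b = 10–25 kcal/day per kg and d = 0–5 kg:

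- smallest shift: b × 0 = 0 kcal/day
- largest shift: 25 × 5 = 125 kcal/day

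The raw difference is negative only when τ < b × d. A second set of assumptions (b = 15–25; 5–15 kg extra weight loss, 20–30% of it lean) puts that threshold between 15 × 5 × 0.2 = 15 and 25 × 15 × 0.3 ≈ 112 kcal/day.

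**Illustrative simulation.** Assumed inputs: 25 versus 20 patients, all with RMR data; b = 20; SD of lean mass change 5 kg; residual SD 150 kcal/day; two-sided alpha 0.05; 4,000 runs per row. The adjusted analysis was a linear model of RMR change on group and lean mass change.

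| τ (kcal/day) | d (kg) | τ − 20d | t-test: mean difference | t-test: estimate < 0 | Adjusted: mean difference | Adjusted: estimate < 0 |
|---|---|---|---|---|---|---|
| 0 | 3 | −60 | −61 | 87% | −1 | 50% |
| +50 | 0 | +50 | +51 | 17% | +50 | 14% |
| +50 | 1.5 | +20 | +19 | 36% | +49 | 14% |
| +50 | 3 | −10 | −10 | 58% | +50 | 15% |
| +50 | 4.5 | −40 | −39 | 77% | +51 | 15% |
| +100 | 3 | +40 | +40 | 23% | +100 | 2% |

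- With no adjusted difference and 3 kg extra lean loss, the t-test was significant for lower RMR with Qsymia in 19% of runs, against a nominal 2.5%.
- With τ = +100 and 3 kg, the sign held on average, but power in the hypothesised direction was 11% for the t-test and 54% for the adjusted model.
- With τ = +50 and 3 kg, the adjusted model itself had only 18% power. Adjustment removes the shift; it does not make this a well-powered comparison.

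**Can the adjusted model be run?** For cases, yes: lean mass comes from a device already scheduled on the RMR visits. For controls this is not established, because follow-up RMR and bioimpedance are not usual care. The time points also do not line up. The Statistical analysis section lists a baseline-to-surgery period, but the schedule has no pre-surgery RMR or bioimpedance visit after baseline. The Secondary Objectives name 3 and 12 months for RMR, while the schedule has 6, 12 and 24.

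**The case against.** **The t-test fits the endpoint.** The objective and the endpoint both speak of change in RMR, and a t-test of change suits that. One phrase in the hypothesis is the outlier, and deleting it would also reconcile the text. This stands as an alternative, but it gives up the question the plan says it wants to answer.

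**Reversal is not established.** A reader might infer that greater lean loss with Qsymia makes the t-test point the wrong way. The documents do not support that. They hypothesise greater weight loss and say nothing about its lean component, and extra lean loss changes the sign only when the adjusted benefit is below b × d. The rows for +50 with 1.5 kg and +100 with 3 kg keep their sign on average. This objection stands in full.

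**Control data may settle the matter first.** If controls have no follow-up RMR or bioimpedance, neither test can be run between groups. This stands as a condition on the fix. A reader might go further and infer that controls certainly lack the data, but the documents show only that these tests were not scheduled as usual care.

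**Conditioning on same-visit lean mass is delicate.** It is a post-treatment variable in a non-randomised comparison, so the adjusted difference should not be read as a total treatment effect. That stands as a caution on interpretation. It is not a reason to avoid the model, because the hypothesis itself asks for this conditioning.

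**It is exploratory.** RMR feeds neither the primary endpoint nor the sample size. This limits the weight of the point.

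**Conclusion.** The mismatch is certain and rests on the text alone: followed as written, the plan does not test its RMR hypothesis. Its numerical consequence is conditional. Under assumed values of 10–25 kcal/day per kg and 0–5 kg extra lean loss, the raw comparison is shifted by 0–125 kcal/day against the hypothesis. It reverses only if the adjusted benefit is smaller than the shift. The documents give no RMR SD or target effect, so they cannot show whether a shift of that size would matter. The plan should be corrected, but the point concerns an exploratory secondary aim of a pilot and does not touch the primary analysis.

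**What to change.** 1. Confirm, before any RMR analysis, whether the historical controls have follow-up RMR and bioimpedance, and at which visits.
2. Where they do, test the hypothesis at the scheduled 6, 12 and 24 month visits with a linear model of follow-up RMR on group, same-visit lean mass, baseline RMR and baseline lean mass. Keep the raw change comparison as descriptive. State that lean mass is a post-treatment variable and that the groups are not randomised.
3. Where they do not, report lean-mass-adjusted RMR change within cases only and make no between-group RMR claim.
4. Align the RMR time points across the Secondary Objectives, the schedule and the Statistical analysis section.

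**Cost.** For cases this is a change of SAP wording, since the device already outputs lean mass. The model estimates five coefficients where the t-test estimates two means, so it uses three more degrees of freedom. The planned total is 40 (20 cases plus 20 controls, Statistical analysis section) or 45 (25 plus 20, sample size section). Residual degrees of freedom therefore fall from 38 to 35, or from 43 to 40. If control data are missing, the cost is larger: a stated between-group hypothesis has to be withdrawn.

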At each physician visit (monthly during phase one and at months 1, 3, 6, 9, 12, 15, 18, and 24 during phase 2) the participant will complete an adverse events questionnaire in addition to the signs and symptoms clinic questionnaire. All adverse events will be reviewed by the study coordinator to clarify any details or questions about the reported event. The PI will then review each adverse event and determine the likelihood that the event was related to the study and whether or not it was an expected event. Study clinicians will also review the medical record at clinic visits to determine if any event or medical care occurring in the interim was related to safety and/or side effects. Any event requiring immediate reporting will be reported as such. All adverse event data will be recorded in RedCAP and tabulated every 6 months for cumulative review. The PI will be responsible for reporting cumulative frequencies of adverse events for those on study drug. Additionally, any derangements in blood

chemistries that are being monitored as part of this study will be cataloged, and frequencies will be reported for all study participants every 6 months.

Participants will be asked to bring in their pill bottles to count any remaining pills at each visit. Missed doses of medication will be noted and any excess medication will be discarded at the refill visits in the hazardous waste containers per clinic protocol. Participants will be provided with only the medication required to provide daily doses until the next scheduled clinic visit.

Some patients enrolled in the study may have diabetes and be on hypoglycemic medications or insulin prior to surgery. As part of usual care, individuals with diabetes are instructed to reduce all diabetes medication by 50% before leaving the hospital after weight loss surgery and are instructed to follow-up with their primary care provider 2 weeks after surgery in order to monitor or modify medications for diabetes and other comorbid conditions such as blood pressure. In addition, discharge documents are sent to each patient's primary care provider either through Wake One or in paper form. Prior to surgery, patients are expected to develop a relationship with a primary care provider.

Statistical analysis

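### The 'ever met' primary endpoint has no common scoring rule or set of weights for treated patients and historical controls, and the visit lists conflict on month 15

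*Combined protocol and SAP*

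**What the plan says.** **Endpoint.** Under Primary endpoint, a patient is an event if three criteria hold at any time in the 24 months after surgery: a plateau (gain, or loss under 3 lb, lasting at least 3 months), BMI above 39.9 kg/m², and a continuing co-morbidity.

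**Treated patients.** Treatment Plan, Treatment Group: "Patients will have standard post-operative surgical follow up at months 1, 3, 6, 9, 12, 18, and 24". The same paragraph adds: "At any point during this course of follow up, a determination can be made that the primary outcome event has occurred".

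**Controls.** Control Group describes matched patients from the same centre who had surgery before the study began, assessed by retrospective review. It does not say which of their visits or weights are used, or who applies the criteria.

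**Month 15.** Safety Monitoring places physician visits "monthly during phase one and at months 1, 3, 6, 9, 12, 15, 18, and 24 during phase 2". The monthly visits of phase one are pre-operative and fall outside the endpoint window; the month-15 visit falls inside it.

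**Weights.** Other measures obtained by chart review: "Weight is measured at every clinic visit and will be captured for the study at the time points in the table below". That table has columns for baseline and months 1, 3, 6, 9, 12, 18 and 24, and none for month 15. Statistical analysis says that weights from clinic visits are uploaded, without listing the visits.

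**The concern.** An endpoint of the 'ever met' kind rises with the number of chances to observe it. The plan describes two ways of finding the event: a prospective determination during follow-up in one group and a later reading of charts in the other. Nothing ties both to the same weights or the same rule.

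The unsettled month-15 visit makes this concrete. It would split the 12-to-18-month gap, which is where the rationale places the usual weight-loss plateau. Suppose a patient loses 6 lb by month 15 and regains 2 lb by month 18. With a month-15 weight, the second interval is a gain and meets the plateau criterion. Without it, the net loss is 4 lb and the criterion is not met. If only one group has that weight, identical courses are classified differently. Matching on age, sex, ethnicity and BMI cannot repair a difference in measurement.

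**Working it through.** **1. The plan's power figure.** Inputs from Sample size justification: "Prior data indicate that the approximate failure rate among controls is 0.7"; treated rate 0.25; alpha 0.05; stated power .840; and, for the test, "We will use an uncorrected chi-squared statistic to evaluate this null hypothesis". Sidedness is not stated; two-sided is assumed.

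Power = Φ[(pC − pT − 1.96·SE0)/SE1], where SE0 uses the pooled proportion and SE1 the separate proportions.

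- 20 v 20: pooled proportion 0.475, SE0 = √(0.475×0.525×2/20) = 0.1579, SE1 = √(0.21/20 + 0.1875/20) = 0.1410. Power = Φ[(0.45 − 0.3095)/0.1410] = 0.8405.
- 25 v 20, as that section states: pooled proportion 20.25/45 = 0.45, SE0 = 0.1492, SE1 = 0.1342. Power = 0.880.

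The stated figure is therefore the power for 20 v 20, which agrees with the 20 cases in Statistical analysis. That mismatch is a separate matter; both sizes are carried below.

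**2. Windows for a plateau call.** Count gaps of at least 3 months between successive visits.

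- Months 1, 3, 6, 9, 12, 18, 24: 3–6, 6–9, 9–12, 12–18, 18–24, so 5 windows.
- With month 15 added: 12–18 becomes 12–15 and 15–18, so 6 windows.

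**3. Direction.** Let a and b be the losses over months 12–15 and 15–18. If a + b < 3 lb, at least one of a and b is below 1.5 lb and so below 3 lb. Every plateau seen over 12–18 is still seen with month 15, and some are added. If the 6-month gap is instead read at the same rate (a + b < 6 lb), at least one of a and b is below 3 lb, so the result is the same. For other extra weights it holds if any two weights at least 3 months apart may be compared.

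**4. Size on the plateau criterion, months 12–18 only.** The documents give no weight-change distribution, so these are assumptions: 3-month changes normal with mean m and SD s, independent, and the 3 lb rule applied to each observed gap. With p = P(change > −3), the share flagged with month 15 is 1 − (1 − p)²; without it, P(N(2m, s√2) > −3).

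| Mean loss per 3 months | SD | With month 15 | Without | Gap (points) |
|---|---|---|---|---|
| 3 lb | 6 lb | 75% | 36% | 39 |
| 6 lb | 6 lb | 52% | 14% | 38 |
| 0 lb | 6 lb | 90% | 64% | 27 |
| 3 lb | 4 lb | 75% | 30% | 45 |
| 3 lb | 8 lb | 75% | 40% | 35 |

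At mean loss 3 lb the mean equals the threshold, so p = 0.5 and the 75% does not move with the SD.

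Independence matters. At mean loss 3 lb and SD 6 lb, with correlation between the two changes:

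| Correlation | With | Without | Gap (points) |
|---|---|---|---|
| 0 | 75% | 36% | 39 |
| 0.5 | 67% | 39% | 28 |
| 0.8 | 60% | 40% | 21 |
| 1 | 50% | 40% | 10 |

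If the 6-month gap is scored at the same rate (under 6 lb), the share without month 15 is 50%. The gap is then 25 points at correlation 0 and zero at correlation 1.

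A different model over the whole 24 months (exponential loss curve, mean total loss 130 lb, SD 30 lb, visit-to-visit SD 2 lb) gives, without v with month 15, 20% v 43%, 6% v 18% and 2% v 10% for time constants of 7, 9 and 12 months. Over time constants of 5 to 12 months and visit SD of 0 to 4 lb, the increase runs from 0 to about 32 points.

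**5. What a shift would cost.** If extra calls raised the observed treated rate above 0.25 (assumed values, controls at 0.70):

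| Treated rate | Power, 20 v 20 | Power, 25 v 20 |
|---|---|---|
| 0.25 | 0.841 | 0.880 |
| 0.27 | 0.800 | 0.844 |
| 0.30 | 0.733 | 0.780 |
| 0.35 | 0.608 | 0.655 |

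**The case against.** The strongest reply is that the most specific text already fixes the weights: study capture is at the table's time points, and month 15 is not one of them. Month 15 appears once, in a sentence about adverse-event and symptom questionnaires. The statement that an event may be called at any point refers to the course of follow-up just described, which has no month 15.

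This stands, and it rules out a stronger reading. A reader might infer that treated patients will have an extra scored weight and that controls have only standard-visit charts. The documents support neither. Use of a month-15 weight is possible but not established, and control charts may hold fewer or more weights than the treated grid.

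It does not remove the point. Weights from clinic visits are uploaded with no list of visits, the real-time determination is not tied to the table, and no text applies one rule to both groups.

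The objection that the size is soft also stands. The 75% v 36% contrast covers one of three criteria in one window, assumes independent changes, and depends on how a 6-month gap is scored. Patients already flagged in another window gain nothing from month 15.

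**Conclusion.** The plan ascertains its primary endpoint differently by group and gives no common rule or set of weights. Its visit lists also contradict each other on month 15. Both follow from the text.

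Bias is conditional. If month-15 or other extra weights are used in the treated group only, the treated event rate can only rise under the scoring in step 3. That works against Qsymia and costs power. A reader might infer that such weights could create a false benefit; extra weights in the treated group would not. The unstated control schedule and the discretion in calling events in real time could distort the comparison as well, in a direction the documents do not determine.

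The size is unknown. On the plateau criterion alone, the illustrations run from 0 to about 39 points, or 45 with SD 4 lb. The effect on the full endpoint would be smaller, because BMI and co-morbidity must also qualify. A modest shift would still matter: an observed treated rate of 0.30 in place of 0.25 takes power from 0.84 to 0.73 at 20 v 20. This should be changed before the endpoint is derived, but it is not a demonstrated bias.

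**What to change.** - Reconcile the Treatment Group section, the measurement table and Safety Monitoring on whether there is a month-15 visit.
- For the primary comparison, classify both groups after follow-up by one fixed written rule, applied only to weights at months 1, 3, 6, 9, 12, 18 and 24. The rule should state how a 6-month gap is read. Where feasible, the assessor should not know the group.
- Report real-time determinations descriptively. They can still inform care as planned.
- Report the number of usable weights per patient by group, so that uneven control charts are visible.

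The cost is a short addition to the endpoint definition and one derived variable. The small downside is that some true plateaus between grid visits go uncounted, in both groups alike.
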